## LIST OF ABBREVIATIONS

AE	Adverse Event
CRC	Colorectal Cancer
DHHS	Department of Health and Human Services
DSMB	Data and Safety Monitoring Board
FDA	US Food & Drug Administration
GCP	Good Clinical Practice
HCP	Healthcare Provider
IRB	Institutional Review Board
ISMMS	Icahn School of Medicine at Mount Sinai
MI	Motivational Interviewing
NIH	National Institute of Health
PPHS	Program for the Protection of Human Subjects
RCT	Randomized Control Study
SAE	Serious Adverse Event
UPR/UPIRSO	Unanticipated Problems Involving Risk to Subjects or Others

## STUDY SCHEMA

**STUDY SUMMARY**

Title	e-Motivación: Developing and Pilot Testing an App to Improve Latinos' Screening Colonoscopy Rates: Aim III
Short Title	N/A
Protocol Number	IRB-18-00344
Phase	N/A
Methodology	Pilot Randomized Control Trial
Study Duration	9 months to conduct pilot study, 6 months to analyze pilot study data and disseminate results.
Study Center(s)	Single-center
Objectives	To begin to examine the efficacy of the e-Motivación app for improving screening colonoscopy uptake among Latinos (results of the pilot study will inform power calculations for a future randomized clinical trial that will formally test the efficacy of the app).
Number of Subjects	80 subjects total (N=40 in control group, N=40 in condition group)
Diagnosis and Main Inclusion Criteria	
 
1. Self-identified as Latino,a,x
 
2. English or Spanish-speaking
 
3. Received a physician referral for a screening colonoscopy
 
4. Has access to a tablet, smartphone, or computer with working internet
 

Study Product(s), Dose, Route, Regimen	N/A
Duration of administration	N/A
Reference therapy	N/A
Statistical Methodology	Contingency tables and t-tests will be performed to determine any differences between the two groups. Using a p value of $\leq 0.15$ , any consistent pattern of correlation for any of the covariates would suggest their inclusion in the primary data analysis model. Effect size estimate: Logistic regression analyses will be used to evaluate an estimate of the efficacy. The model will include any covariates that differentiate the intervention and control groups. The effect size of the treatment group will be used as an indicator to inform power calculations for a future RCT. The power calculations will inform the appropriate sample size needed for the RCT.

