### 2.4 Endpoints

2.4.1 Screening colonoscopy completion status in medical charts six months after participants complete the consent for the study will be used as a proxy for efficacy of the e-Motivación app in improving screening colonoscopy uptake among Latinos. In our previous study with a similar sample, less than 10 of 900+ participants reported completing the colonoscopy at a different hospital. As such, for the proposed project, if the medical chart does not report that a colonoscopy was completed, the colonoscopy will be documented as "not completed".

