**4.6 Duration of Follow Up**

Six months following the consent to take part into the study, medical charts will be reviewed to determine colonoscopy completion status.

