**5.4 Time and Events Table**

Research Timeline [Aim III]	Months 1-3	Months 4-6	Months 7-9	Months 10-12	Months 13-15
Recruitment	X	X	X		
Informed Consent	X	X	X		
Baseline data (demographics & medical history)	X	X	X		
Review of medical charts (colonoscopy completion status)			X	X	X
Analyze pilot study data					X
Disseminate results					X

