**6.0 Measurement of Effect**

Screening colonoscopy completion status (in medical charts) six months after the patient expressed informed consent to participate in the study will be the proxy for efficacy of the e-Motivación app in improving screening colonoscopy uptake among Latinos. If the medical chart does not report that a colonoscopy was completed, the colonoscopy will be documented as "not completed". This decision is informed by a study that we have conducted with a similar sample, where less than 10 out of 900+ participants reported completing the colonoscopy at a different hospital.

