### 10.0 STATISTICAL CONSIDERATIONS

#### 10.1 Study Design/Study Endpoints

This pilot study is a behavioral research Randomized Control Trial. A previously used English/Spanish questionnaire is administered to assess demographics and medical history of participants. Stratified randomization (per language, English or Spanish) assigns participants to either the e-Motivación condition arm or control arm.

Participants in both groups will be asked to complete their respective tasks on their personal device of choice (going through the e-Motivación App or watching the general health informative video). To determine colonoscopy completion status, patients' medical charts are to be reviewed six months following patient's consent to participate in the study.

---

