The severity of an adverse event is graded as follows:

- Mild (grade 1): the event causes discomfort without disruption of normal daily activities.
- Moderate (grade 2): the event causes discomfort that affects normal daily activities.
- Severe (grade 3): the event makes the patient unable to perform normal daily activities or significantly affects his/her clinical status.
- Life-threatening (grade 4): the patient was at risk of death at the time of the event.
- Fatal (grade 5): the event caused death.

8. *Describe procedures that will be used to assure data accuracy and completeness.*

Study data will be entered by a Research Coordinator trained to enter data into a password-protected, secure database on REDCap. To ensure the validity and integrity of study data, the PI will oversee all data management responsibilities. Data entry, level of accuracy and percentage of error in data entry will be discussed with the study team on a regular basis. Monthly meetings (either in person or via video/telephone conference) will be held with the entire study team.

Thorough training of Research Coordinators is also designed to ensure adequate protection of human subjects. All Research Coordinators will receive all required training and certification in Mount Sinai's human subjects in research. Research Coordinators will be required to participate in a training program designed to ensure that they administer the interviews and evaluate participant responses in a sensitive manner. Research Coordinators will be trained to speak clearly and audibly and let participants determine the pace of the interview.

Protocol compliance will be monitored at the weekly research staff meetings. The PI will meet with the study staff on a weekly basis to train and ensure adherence to the intended protocol. The PI will be responsible for updating all investigators regarding any study related issues that arise of that need to be addressed.

The medical chart abstraction will be conducted by a research team member. A second research team member will review 20% of the medical charts to confirm accuracy.

9. *Should a temporary or permanent suspension of your study occur, in addition to the PPHS, to whom (NIH, FDA, sponsor, IRB) will you report the occurrence?*

IRB and Program Officer of the National Institute On Aging/NIH/DHHS

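### Does the 15-month schedule leave too little time to analyse the six-month outcome, and does it matter that the Summary and the timeline table split those months differently?

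*Combined protocol and SAP*

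**What the plan says.** The Study Summary gives the duration as "9 months to conduct pilot study, 6 months to analyze pilot study data and disseminate results".

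The Time and Events Table in section 5.4 works in three-month blocks:

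- Recruitment and the row "Informed Consent" are marked in months 1-3, 4-6 and 7-9.
- Chart review for colonoscopy status is marked in months 7-9, 10-12 and 13-15.
- "Analyze pilot study data" and dissemination are both marked in months 13-15 only.

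The outcome is timed the same way wherever it is defined. Section 2.4 has "Screening colonoscopy completion status in medical charts six months after participants complete the consent for the study". Section 4.6 has "Six months following the consent to take part into the study, medical charts will be reviewed to determine colonoscopy completion status". Section 6.0 measures status "six months after the patient expressed informed consent to participate in the study". Section 10.1 says that "medical charts are to be reviewed six months following" consent. Sections 2.4 and 6.0 add that a chart with no record of a completed procedure counts as a non-completion.

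For quality control, section 11.5.1 provides weekly chart-review reports and states: "A second research team member will review 20% of the medical charts to confirm accuracy". Section 10.3, the analysis plan, does not say when the final analysis may begin.

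**The concern.** Two things look wrong. First, the documents agree on the 15-month total but divide it differently: six months for analysis and dissemination in the Summary, three in the table. Neither reading of the Summary's nine months of conduct fits easily. If conduct includes follow-up, consent would have to end by month 3, yet the table recruits to month 9. If conduct means enrolment and the one-time intervention, the six months labelled as analysis are also the last participant's follow-up.

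Second, with consent to the end of month 9 and a six-month outcome, the last result falls due just as the timeline ends. Final abstraction, analysis and dissemination would have to happen in no time at all.

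The statistical worry is what a team might do to meet the date. If the data were closed early and charts still inside their six months were coded as non-completions, completion rates would be understated. If those participants were left out, the analysed sample would fall below 80. Either would weaken the effect estimate that is meant to size the later trial, which is this pilot's purpose.

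**Working it through.** **Inputs**

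- Summary: 9 months of conduct, 6 months of analysis and dissemination.
- Section 5.4: consent in months 1-9, chart review in months 7-15, analysis and dissemination in months 13-15.
- Sections 2.4, 4.6, 6.0 and 10.1: outcome at consent + 6 months.
- Section 10.2: 80 participants.
- Section 11.5.1: second review of 20% of charts.

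**The plan's own total.** 9 + 6 = 15 months, which matches the last column of the table. The analysis and dissemination period is 6 months in the Summary and 15 - 12 = 3 months in the table.

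**Time left after the last outcome.** Slack = 15 - (month of last consent + 6).

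| Last consent (end of month) | Outcome due (end of month) | Months left |
|---|---|---|
| 6 | 12 | 3 |
| 7 | 13 | 2 |
| 8 | 14 | 1 |
| 9 | 15 | 0 |

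A mark under months 7-9 does not say that consent runs to the last day of month 9. The slack is therefore 0 to 3 months, and zero is its lower end.

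**Outcomes not yet due at earlier dates.** The documents give no accrual pattern, so three are assumed for the shares consenting in months 1-3 / 4-6 / 7-9. Not due at month t = share consenting after month t - 6.

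| Assumed accrual | Not due at end of month 9 | Not due at end of month 12 |
|---|---|---|
| Uniform (1/3 each) | 2/3 × 80 = 53 | 1/3 × 80 = 27 |
| 50/30/20% | 50% × 80 = 40 | 20% × 80 = 16 |
| 20/30/50% | 80% × 80 = 64 | 50% × 80 = 40 |

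These counts would measure damage only if a final analysis were run on those dates. No section schedules one then: the table marks chart review, analysis and dissemination in the same last block without ordering them.

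**How much follow-up lies beyond month 9.** With even accrual within each quarter, the average follow-up after month 9 is 0, 1.5 and 4.5 of the 6 months for the three consent quarters.

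- Uniform: (0 + 1.5 + 4.5)/3 = 2.0; 2.0/6 = 33%.
- 50/30/20%: 0.3 × 1.5 + 0.2 × 4.5 = 1.35; 1.35/6 = 22.5%.
- 20/30/50%: 0.3 × 1.5 + 0.5 × 4.5 = 2.70; 2.70/6 = 45%.

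Under all three patterns, most follow-up time is complete by month 9.

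**Workload at the end.** At a uniform rate, 80/9 = 8.9 charts fall due in the final month. The second review covers 0.20 × 80 = 16 charts. By the end of month 12 the charts already due number 80 - 27 = 53, 80 - 16 = 64 or 80 - 40 = 40 under the three patterns, so the 16 can be drawn and checked before the last ones come in. Section 11.5.1 does not make that check wait for the final chart.

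**What rewriting the schedule would cost.**

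- Placing analysis after month 15 gives 15 + 3 = 18 or 15 + 6 = 21 months.
- Keeping 15 months with three clear months for analysis means closing recruitment at month 6. That needs 80/6 = 13.3 consents a month instead of 8.9, which is 50% faster. At the nine-month rate only 8.9 × 6 = 53 of 80 would be enrolled by then.

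**The case for a change.** The strongest case for a change is that the analysis plan contains no rule on when the data are closed and does not say how to treat an outcome not yet due, while sections 2.4 and 6.0 turn an absent record into a failure. Rolling chart review helps with early participants but cannot bring forward an outcome due at the end of month 15. A single sentence saying that analysis waits for the last six-month review would cost nothing.

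Part of this stands. The six-versus-three mismatch is real, and if consent runs to the end of month 9 the stated duration cannot be met with complete outcomes.

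The step from a tight calendar to a biased estimate does not stand. The absent-record rule belongs to an endpoint read at six months, so applying it to a chart still inside that window would depart from the endpoint definition. Section 11.6 requires the study to be run as the approved protocol describes. The extra sentence would only write down what an analyst must already do to obtain the defined endpoint for all 80 participants.

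**Conclusion.** No change to the plan is needed. The mismatch is a slip in labelling. The totals agree at 15 months, and the Summary's nine months match the table's recruitment rows if its six months are read loosely as covering the remaining chart review, analysis and dissemination.

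The tight schedule is a boundary case: 0 to 3 months remain after the last outcome, depending on when in months 7-9 the last participant consents. If consent does run to the end of month 9, following the protocol means the study ends later than stated. The endpoint, the 80 participants and the logistic model are unaffected.

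Relabelling the Summary line or the table would change no result. The substantive alternatives are not free: 3 to 6 more months, or recruitment 50% faster. Closing recruitment at month 7 or 8 would leave 2 or 1 months, again at the price of quicker accrual.

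This conclusion assumes that charts are read at six months, as every section defining the outcome requires. The counts of outcomes not yet due rest on assumed accrual patterns and describe dates on which no final analysis is planned.

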## 1.0 BACKGROUND AND RATIONALE

### 1.1 Disease Background

**Colorectal Cancer and Aging.** The risk of developing colorectal cancer (CRC) directly increases with age, with 89% of all CRC occurring in individuals over the age of 50. The median age of a colon cancer diagnosis is 68 in men and 72 in women; the median age for rectal cancer is 63 in both men and women. Given the link between age and CRC, the American Cancer Society, the U.S. Multi-Society Task Force on Colorectal Cancer, and the American College of Radiology recommend that average risk people begin screening for CRC at the age of 50 and continue until at least the age of 75. Of the recommended CRC screening tests, a colonoscopy is considered the gold standard because it allows for both the detection and removal of precancerous and cancerous growths. Epidemiological research has found an association between increased screening colonoscopy rates and reduced mortality rates.

**Colorectal Cancer and Latinos.** Among Latinos, a fast growing population, CRC remains the third leading cause of cancer death in the U.S. Compared to non-Latino whites, Latinos are less likely to be diagnosed with localized CRC and more likely to be diagnosed with advanced stage disease. Given this disparity, it is critical to increase this population's participation in CRC prevention efforts. Although screening colonoscopies can detect and prevent CRC, more than half of Latinos have not received a screening colonoscopy within the recommended time frame (one colonoscopy per ten years). Among uninsured Latinos, only a staggering 11% have received any type of recent CRC screening. It is critical to increase Latinos' screening colonoscopy rates in order to the unequal burden of CRC in the Latino community.

**Motivational Interviewing.** Motivational Interviewing (MI), a brief client-centered behavioral intervention, may improve Latinos' screening colonoscopy uptake. Drawing from Self-Determination Theory (SDT), MI helps increase competence, autonomy, and relatedness in order to promote behavioral change. MI involves four sequential processes: (1) *engaging* the patient in the intervention; (2) *focusing* the goal of the intervention; (3) *evoking* motivations for change; and, (4) *planning* for change. Within this framework, MI implements techniques (e.g., decisional balance) to support behavior change. MI was originally developed to treat substance use, and extensive research supports its efficacy for treating drug, alcohol, and nicotine use. More recently, MI has proven efficacious for improving health behaviors such as diet, exercise, and medication adherence. A meta-analysis found that MI had a significant, moderate effect ( $d=0.53$ ) for improving health behaviors when compared to a no treatment/placebo control group. Moreover, research has found that the effects of MI are long-lasting (>2 year follow up). Extensive evidence supports the use of MI with Latinos. For example, research with exclusively or predominantly Latinos/Hispanic samples have found MI efficacious for managing diabetes, decreasing drug use/needle sharing, quitting smoking, and decreasing alcohol use. In fact, a 2005 review found MI to yield larger effect sizes with minorities, compared to non-minority whites.

**MI for Colonoscopy.** Preliminary research has found MI to be efficacious for improving screenings for HIV, breast cancer, skin cancer, and cervical cancer. A recently published study examining the efficacy of MI to improve CRC screening uptake produced promising results, though non-significant ( $OR=1.6$ ,  $CI=0.9, 3.0$ ). Notable problems with this study may have limited the effects of MI. Most critical, not all MI interventionists were proficient in MI in the beginning stages of the study. Additionally, the intervention implemented techniques (e.g., discussing ambivalence when it was not clinically indicated) that may have been counterproductive. A systematic review of the literature yielded that

MI shows strong promise for improving health screening behaviors, including several cancer screenings.

**1.2 Study Agent(s) Background and Associated Known Toxicities**

N/A

**1.3 Other Agents**

N/A

**1.4 Rationale**

**MI as an E-Health Intervention.** Traditionally, MI is delivered live, where individuals meet with a professional either in person or over the telephone. Although efficacious, live-MI is not without limitations. Of greatest concern, live-MI requires staffing and economic resources, limiting its potential for wide dissemination. As such, many studies have examined the efficacy of e-MI, that is MI interventions delivered via electronic media (e.g., smartphone). This line of research began with the “Drinker’s Checkup”, an e-MI intervention designed to reduce alcohol use in problem drinkers. Extensive research supports the efficacy of this intervention and it is currently listed in the Substance Abuse and Mental Health Administration (SAMSHA’s) National Registry of Evidence-based Protocols and Programs (NREPP). Due to its proven efficacy, the Drinker’s Checkup can be accessed online for clinical use and it has been widely disseminated both nationally and internationally.

Although e-MI cannot replicate the nuances of live-MI, with advancing technology (e.g., algorithm based tailoring), e-MI is able to capture many of the essential components of live-MI, thus contributing to its widely proven efficacy.

**Advantages of e-MI versus live-MI.** There are both clinical and research advantages to using e-Health interventions, such as e-MI, as compared to live interventions. The *clinical* advantages of e-Health interventions include: **(1) High Technology Use:** E-health interventions are timely given the ubiquity of technology use in the U.S. According to a recent report from the U.S. Census, in 2015, 78% of households had a computer and 75% had a handheld computer (e.g., smartphone). The PEW Internet & American Life Project’s 2015 statistics reported that 84% of Latino adults use the Internet and 80% of Latino adults access the Internet via smartphone or tablet. In recent years, the digital divide between Latinos and non-Latino whites has significantly narrowed, largely due to the increases in Internet use among immigrant Latinos and Spanish-speaking dominant Latinos. In fact, from 2009 to 2015, the rate of immigrant Latinos who use the Internet increased from 51% to 78% and the rate of Spanish-speaking dominant Latinos who use the Internet increased from 36% to 74%. **(2) High Reach:** E-Health interventions have the potential for wide dissemination because they can be accessed from multiple locations and at convenient times, thus overcoming common barriers to receiving health interventions (e.g., limited transportation). E-Health interventions may be particularly useful for individuals of low socioeconomic status as they are often confronted with access barriers such as having limited transportation. **(3) Privacy:** E-Health interventions can be accessed in private locations, maximizing anonymity and privacy. Research has found that individuals are more willing to disclose personal information when interacting with a computerized device versus a person. Privacy may be particularly important with regard to potentially embarrassing health content, such as that surrounding a colonoscopy. **(4) Low Cost:** E-Health interventions do not require the hiring or training of staff thus reducing costs. The *research* advantages to e-Health interventions include: **(1) Standardization:** E-Health interventions are highly standardized, thereby minimizing variance and maximizing internal validity. **(2) Storage and Backup:** E-Health interventions can be linked to secure online databases that are regularly backed up thereby

eliminating errors in data entry and maximizing data security. **(3) Tailored by Language:** E-health interventions can be programmed to be offered in multiple languages (e.g., Spanish and English) to address a wide range of patient populations.

**e-MI to Improve Latinos' Screening Colonoscopy Uptake.** Despite the strong promise of MI for improving screening colonoscopy uptake, and the advantages of e-MI, no study to date has examined the efficacy of e-MI to improve Latinos' screening colonoscopy uptake. This study pilot tests an e-MI intervention, e-Motivación (e-Motivation), to help improve Latinos' screening colonoscopy uptake. This line of research will increase our understanding of efficacious interventions to improve Latinos' CRC screening rates. It will also provide power calculations for a future RCT that will formally examine the efficacy of the e-Motivación app for improving Latinos' screening colonoscopy uptake. This program of research can help increase Latinos' colonoscopy uptake and, in doing so, reduce CRC screening disparities.

